## 12.0 AGENT INFORMATION

### Imatinib Mesylate

#### 1. Chemistry

Imatinib mesylate, a phenylaminopyrimidine derivative, is designated chemically as 4-[(4-12 Methyl-1-piperazinyl)methyl]-N-[4-methyl-3-[[4-(3-pyridinyl)-2-pyrimidinyl]amino]-13 phenyl]benzamide methanesulfonate and its structural formula is:

It was originally found as an inhibitor of the tyrosine kinase activity of the *BCR-ABL1* fusion gene (oncoprotein), the product of the Philadelphia chromosome. Imatinib mesylate has also shown activity in blocking the tyrosine kinase activity of c-kit, the stem-cell factor receptor, and of PDGFR, the platelet-derived growth factor receptor and cellular events mediated by PDGF and SCF. Our studies have demonstrated that it also has significant blocking activity of Syk, the tyrosine kinase that phosphorylates band 3 in erythrocytes.

#### 2. Mechanism of Action

Imatinib (ST1571), a phenylaminopyrimidine derivative, is a selective inhibitor of the tyrosine kinase activity of the *BCR-ABL1* fusion gene (oncoprotein), the product of the Philadelphia chromosome. Imatinib mesylate has also shown high activity in blocking the tyrosine kinase activity of stem-cell factor receptor (SCF), c-kit and platelet-derived growth factor PDGF and cellular events mediated by PDGF and SCF. The ability of imatinib to inhibit *BCR-ABL1* tyrosine kinase activity is related to its occupancy of the kinase pocket of the protein, which blocks access to ATP and prevents substrate phosphorylation inhibiting BCR- ABL dependent cellular proliferation. Imatinib has caused apoptosis or arrest of growth in hematopoietic cells expressing *BCR-ABL1*.

Imatinib is well-absorbed after oral administration; maximum plasma concentrations are achieved 2 to 4 hours after administration. The elimination half-lives of imatinib and its major active metabolite, the N-desmethyl derivative, are approximately 18 and 40 hours, respectively. The elimination half-life of the parent drug in children is approximately 15 hours. Imatinib is approximately 95% protein-bound, mostly to albumin and alpha-1- acid glycoprotein. CYP3A4 is the major enzyme responsible for metabolism. CYP1A2, CYP2D6, CYP2C9, and CYP2C19 play minor roles in metabolism. Drugs metabolized by these same enzymes should be avoided or used with caution to avoid unwanted drug interactions. Severe hepatic impairment (bilirubin >3-10 times ULN) increases AUC by 45% to 55% for imatinib and its active metabolite, respectively. Elimination is predominately in the feces, mostly as metabolites.

#### 3. Supplier

Mylan Pharmaceuticals

## **13.0 CRITERIA FOR REMOVAL FROM PROTOCOL THERAPY**

1. Adverse Events requiring removal from study
2. Refusal of further protocol therapy by patient/parent/guardian.
3. Non-compliance that in the opinion of the investigator does not allow for ongoing participation, including <70% of drug prescribed being taken. Compliance will not be contingent on completion of the pain journal as this not the primary endpoint of the study.
4. Physician determines continued protocol therapy is not in the patient's best interest.

Patients who are off protocol therapy are to be followed until they meet the criteria for Off Study (see below). Ongoing adverse events, or adverse events that emerge after the patient is removed from protocol therapy, but within 30 days of the last dose of investigational agent, must be followed and reported via RDE and AERS (if applicable). Follow-up data will be required unless consent is withdrawn.

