### 4.3. Endpoints

- 4.31 Primary Endpoints:
  - a. Biochemical Effects to RBCs (see Section 17)
    - i. Band 3 Phosphorylation
    - ii. Microparticle Release
  - b. Functional RBC analysis (see Section 17)
    - i. Percent Irreversibly Sickled Cells at Month 6
    - ii. Ektacytometry
    - iii. OxygenScan to evaluate for altered susceptibility to sickling
- 4.32 Secondary Endpoints:
  - a. Clinical Outcomes

- i. Vaso-occlusive Crisis (VOC)
  - i. Defined as an acute episode of pain lasting greater than 24 hours, with no medically determined cause other than a vaso-occlusive event that resulted in treatment with oral or parenteral opiate agents and/or parenteral nonsteroidal anti-inflammatory agents.
  - ii. To be documented in pain diary by patient/guardian and reviewed at each visit
  - iii. Measured by pain scale (1-10) or Wong-Baker Faces scale based on age:
- ii. Acute Chest Syndrome
  - i. Defined as respiratory distress (hypoxia, shortness of breath, chest pain, tachypnea) with evidence of an infiltrate on chest x-ray
  - ii. Will be reviewed at each visit, as well as extracted from the EMR by each site
- iii. Opioid Use
  - i. Defined as both oral and parenteral opioid use
  - ii. Oral use will be documented in pain diary by patient/guardian and reviewed at each visit.
  - iii. Frequency of refills and parenteral opioid use will be extracted from the EMR by each site
- iv. Hospitalizations
  - i. Defined as an emergency room or clinic visit resulting in an inpatient admission or observation for a sickle cell-related event (e.g. vaso-occlusive pain, acute chest syndrome, etc).
  - ii. Will be reviewed at each visit, as well as extracted from the EMR by each site
- v. Assessment of tolerability and evaluation for any toxicities of imatinib in patients withSCA

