## 5.0 INVESTIGATIONAL PLAN

### 5.1 Study Design

This will be an open label nonrandomized pilot study to determine the effect of imatinib on band 3 phosphorylation, microparticle release from sickle RBCs, and percent irreversibly sickled cells obtained from adolescent and young adult patients with Hemoglobin SS Disease or S-Beta 0 Thalassemia before, during, and after 6 months of treatment with imatinib. We will also look at clinical outcomes during treatment (pain) and before treatment. Clinical outcomes before treatment will be collected via retrospective chart review.

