Patients will be given a copy of the "Patient Pain Journal" at each visit which will need to be completed and returned at the next visit. This journal should be reviewed with the treating physician and/or research nurse at each clinic appointment while on study. Patients should be instructed to use the journal to record any occurrence of pain episodes (see definition in Section 5.3), the duration, and necessary interventions. They will be asked to score their pain on a scale of 1-10. Additionally, it will be used to record the date and time of each imatinib dose as well as observed side effects and supportive treatments used while on study.

Opioid use, hospitalizations, and occurrence of acute chest syndrome (see definitions in Section 5.3) will be reviewed at each study visit, as well. This information will also be extracted from the EMR at each site to confirm patient/guardian report.

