## 15.4 Efficacy evaluation

Descriptive statistics will be calculated for all endpoints before, during, and after treatment. Changes before and 6 months after treatment in biochemical endpoints will be tested with two-sided paired t-tests. This analysis will be supplemented with single group repeated measures ANOVA to test for effects over time since there are 3 measures on treatment. Many secondary endpoints are counts (e.g. frequency of refills of opioids, number of hospitalizations). Depending on the distributions of these outcomes, we will either: 1) dichotomize and compare with McNemar's test; 2) treat as ordinal and compare with a Cochran-Mantel-Hazensel type test; or 3) treat as continuous and conduct either paired t-test or Wilcoxon signed rank tests. Since the pain measure will depend on age, we will only statistically analyze when there are at least 6 participants using a single-group repeated measures ANOVA model. Otherwise, only graphical descriptions will be used.

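### On-treatment vaso-occlusive crises rest on an optional journal with no missing-journal rule, while baseline crises come from charts, so the before/after comparison can be biased in either direction

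*Combined protocol and SAP*

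**What the plan says.** Section 4.3 defines a VOC by pain lasting more than 24 hours and by its treatment: "a vaso-occlusive event that resulted in treatment with oral or parenteral opiate agents and/or parenteral nonsteroidal anti-inflammatory agents". An episode managed at home with oral opiates can therefore qualify. The stated source is the diary: "To be documented in pain diary by patient/guardian and reviewed at each visit".

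For acute chest syndrome and hospitalizations the same section says "Will be reviewed at each visit, as well as extracted from the EMR by each site". Opioid refills and parenteral opioid use are also taken from the electronic medical record (EMR), while oral opioid use is documented in the diary. Section 6.0 names opioid use, hospitalizations and acute chest syndrome and adds "This information will also be extracted from the EMR at each site to confirm patient/guardian report". VOC is in neither EMR list.

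On the journal itself, Section 6.0 says "Patients will be given a copy of the 'Patient Pain Journal' at each visit which will need to be completed and returned at the next" monthly appointment. Section 13.0, on non-compliance as a reason for removal from therapy, says "Compliance will not be contingent on completion of the pain journal as this not the primary endpoint of the study".

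For the comparison period, Section 5.1 says "Clinical outcomes before treatment will be collected via retrospective chart review". Section 15.4 offers several methods for count endpoints, depending on their distribution: McNemar's test after dichotomizing, an ordinal Cochran-Mantel-Haenszel-type test, or "treat as continuous and conduct either paired t-test or Wilcoxon signed rank tests". It gives no exposure term, no rule for a missing journal and no order of precedence among sources.

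**The concern.** The two sides of the before/after VOC comparison are observed by different means, and only one of them can lose journal months. If a patient stays on treatment but returns no journal for a month, and nobody recovers that month's crises at the visit, the patient's on-treatment count is lower and nothing in the analysis records that the month was unobserved. A paired test on raw counts reads this as fewer crises.

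The chart side has a different weakness. A crisis treated at home with oral opiates may leave no chart entry, although a prospective journal could catch it. That makes the baseline look too low.

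What is at stake is the secondary aim on VOC frequency (Section 4.2) and, to a lesser degree, the journal-recorded oral opioid summary. Section 2.0 says the results will inform a later Phase II-B trial of clinical outcomes, so the VOC estimate is likely to be used. The mechanism concerns patients who remain on treatment and on study. It is separate from early exit and from the choice of look-back window.

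**Working it through.** **The plan's own figure.** No power or effect size is stated for VOC. The only efficacy power figure is for microparticles (Section 15.1). SD of the difference = 75,000 × √(2 × (1 − 0.5)) = 75,000, and d = 70,000/75,000 = 0.933. The noncentrality is 0.933 × √20 = 4.17 on 19 df, against a critical t of 2.861 at two-sided alpha 0.01. Power is 88.98%, which agrees with the stated 89%. This point does not touch that figure.

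**Inputs.**
- From the documents: 20 treated patients; 6 months of treatment with monthly visits; at least 2 VOCs in the prior year at entry (Section 5.2.1), so a minimum of about 1 per 6 months.
- Assumed, because the documents give no value: *m*, the share of journal months missing; *c*, the share of true VOCs that chart review captures before treatment; *r*, the share of VOCs in missing months recovered from visit history; and VOC rates above the entry minimum.

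**Apparent reduction with no drug effect**, if unrecovered months add no events:

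apparent reduction = 1 − [1 − m(1 − r)] / c

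With c = 1 and r = 0 this is simply *m*: one journal of six missing gives 1/6 = 17%, two of six give 2/6 = 33%. With r = 0:

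| m | c = 1 | c = 0.85 | c = 0.70 |
|---|---|---|---|
| 0.1 | 10% fall | 1 − 0.9/0.85: 6% rise | 1 − 0.9/0.7: 29% rise |
| 0.2 | 20% fall | 1 − 0.8/0.85: 6% fall | 1 − 0.8/0.7: 14% rise |
| 0.3 | 30% fall | 1 − 0.7/0.85: 18% fall | 1 − 0.7/0.7: no change |

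With r = 0 the sign turns at m = 1 − c. Below that the bias works against imatinib, above it in favour.

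**Chance of a significant false benefit.** Simulation: 20 patients, 6 months against 6 months, gamma-Poisson counts (shape 2), same true rate in both periods, missing months adding no events, two-sided paired t-test at 0.05. The nominal rate in the favourable direction is 2.5%. With complete charts and no recovery:

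| VOCs per 6 months | 10% missing | 20% | 30% | 40% |
|---|---|---|---|---|
| 3 | 7% | 16% | 32% | 51% |
| 1.5 | 6% | 11% | 19% | 32% |
| 1 (entry minimum) | about 4% | about 9% | about 16% | about 25% |

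**Sensitivity at 3 VOCs per 6 months.**
- Charts capture 85%: about 4% false benefit at 20% missing and 12% at 30%.
- Charts capture 70%: the apparent change at 10% or 20% missing is a rise, not a fall.
- Charts complete, half of the VOCs in missing months recovered: 5%, 8% and 13% at 10%, 20% and 30% missing. With 80% recovered: 3%, 4% and 5%.

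**Effect of the remedy.** With observed months as the denominator, complete charts and missingness unrelated to pain, the false-benefit rate returned to 2% to 4% in every setting tried. That denominator does not repair incomplete charts.

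**The case against.** The strongest reply is that two natural inferences go beyond the documents.

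A reader might infer that the plan scores a month without a journal as crisis-free. No passage says so. Section 15.4 is silent, and its count examples are opioid refills and hospitalizations. What stands is narrower: a raw event count with no denominator produces that result by default unless someone intervenes.

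A reader might also infer that the bias must favour imatinib because charts have no gaps. Charts have no journal gaps, but the VOC definition admits oral-opiate episodes that a chart review may miss. At plausible capture rates the two biases can cancel or the sign can reverse. That does not rescue the comparison, because one unknown bias is not a correction for another.

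Other routes could recover events. History is scheduled at every monthly visit (Sections 6.0 and 11.0), there are weekly safety contacts in the first two months, and EMR extraction covers sickle-related admissions and parenteral opioids. Section 18.4 names the medical record as a general data source. These could shrink the problem considerably, as the recovery figures show. None is named as a source of VOC counts, however, and no VOC item at visits is described.

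The oral opioid summary is better protected than VOC, because Section 6.0 also sends opioid use to EMR confirmation and refills come from the EMR.

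Finally, the size is in part built in: scoring a given share of months as empty must give that apparent fall. The figures show sensitivity and do not predict the result. Only the paired t-test, one of the permitted methods, was simulated.

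**Conclusion.** The concern holds in a limited form. On-treatment VOC relies on a journal that compliance does not depend on, with no EMR back-up and no missing-journal rule. Baseline VOC comes from charts, and the planned tests take no account of observed time. Unrecovered missing months push toward imatinib and incomplete charts push away from it; the net direction is not fixed.

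At the unfavourable end (charts complete, nothing recovered) the apparent fall equals the missing share. For 10% to 40% missing, the false-benefit rate is then about 7% to 50% at 3 VOCs per 6 months and about 4% to 25% at the entry minimum. It is much lower if charts are incomplete or history recovers events. Journal return, chart capture and recovery are all assumed.

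Section 13.0 should not be read as an error in itself: it is a compliance criterion, and the gap lies in the data sources and the analysis. VOC is a secondary endpoint, so the five primary endpoints and the 89% power are unaffected. The change should be made, but the primary conclusions do not depend on it.

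**What to change.** 1. At each existing monthly visit, record on the case report form whether a VOC has occurred since the last visit (yes/no, dates) and whether the journal was returned (yes/no).
2. Extract medically attended VOCs from the EMR by the same rule before and during treatment, and use these as the like-for-like before/after comparison.
3. In Section 15.4, analyse journal- or history-based VOC as a rate per observed day, for example by Poisson or negative binomial regression with log observed days as offset and clustering by patient. Treat a month with neither journal nor visit history as unobserved, not zero, and report the percentage of treatment days covered.
4. Apply the same denominator to the journal-recorded oral opioid summary, noting that refills and parenteral use already come from the EMR.

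Step 3 alone leaves the chart-versus-journal mismatch in place, so step 2 is needed as well. Step 3 also assumes that missing months are unrelated to pain; reporting coverage lets a reader judge that.

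The cost is analysis-plan wording, two form items at visits that already take a history, a little more chart abstraction and slightly wider intervals. The Section 13.0 compliance rule need not change.

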## **14.0 OFF STUDY CRITERIA**

1. Thirty days after the last dose of the investigational agent.
2. Death
3. Lost to follow-up
4. Withdrawal of consent for any further data submission.
5. Enrollment onto another therapeutic study

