## **6.0 TREATMENT PROGRAM**

All patients with sickle cell anemia will be treated in the same group. There will not be a randomization.

Patients will receive Imatinib orally once daily for 6 months.

The starting dose for subjects will be 340 mg/m^2/day with a maximum dose of 600 mg daily. Drug doses will be rounded to nearest 50 mg according to the dosing table in Appendix A. Dosing should be based on the body surface area (BSA) obtained at each clinic appointment. Drug will be dispensed as a 30-day supply at each visit. Patients will be asked to bring the prescription bottle with them to each visit to assist with monitoring compliance.

Clinic visits will occur at initiation of imatinib and then every 30 days +/- 7 days. Monthly visits will consist of interim history, assessing for adverse side effects and compliance. Participants will be asked to have blood drawn (see Section 11) 2 weeks +/- 3 days after initiation of the drug. Additionally, during the first two months of drug administration, patients will be called or texted a survey link weekly for follow-up safety assessments, except for the participant's in-clinic visits at week 2, 4 and 8. The survey link will come via an app, called Twilio, that allows REDCap the capability to send SMS text messages to survey respondents. If the patient is unable to be reached by phone for at least 3 of the 4 weekly assessments each month, they will be asked to be seen in clinic for a safety assessment. If the patient is unable to do so, they will be removed from protocol therapy for protocol non-compliance. The 1 month, 3 month, 6 month, and 1-month off-therapy visits will consist of a comprehensive history and physical

exam, as well as laboratory and diagnostic studies documented in Section 10. The other visits (2, 4 and 5-month visits post treatment initiation) will be research-nurse visits, with a provider available to sign the next month's prescription.

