## **6.1 Dosage:**

Mylan will supply Imatinib as 100 mg tablets packaged in bottles for an exposure period of up to 6 months or so long as the patient remains on study. The starting dose for subjects will be 340 mg/m^2 with a maximum dose of 600 mg daily. Tablets can be broken in half, and therefore, drug doses will be rounded to nearest 50 mg according to the dosing table in the Appendix A. Dosing should be based on the body surface area (BSA) obtained at each clinic appointment.

The prescribed dose should be administered at the same time each morning, orally, with a meal and a large glass of water. Patients should keep normal eating habits, however a low-fat (i.e. continental) breakfast is recommended and avoiding xanthine (e.g. caffeine) or grapefruit containing food or beverages. If vomiting occurs > 15 minutes after administration of the dose, no additional trial medication should be taken that day in an effort to replace the material that has been vomited.

In the absence of dose limiting toxicity (DLT), patients may receive a total of 6 months of therapy. Continuing treatment beyond this period will be at the discretion of the investigator and may become the financial responsibility of the patient if no alternative method of obtaining or paying for the drug can be identified at that time. Medication labels will comply with the legal requirements of the US and will be printed in English. The storage conditions for Imatinib will be described on the medication label. Bottles must be stored in a safe, secure location.

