## 9.0 DOSE MODIFICATIONS FOR ADVERSE EVENTS

**The study PIs must be notified of any dosage modification.**

- 1. Dose modifications for hematological toxicity** (Of note, such adverse events have been observed in patients with CML (chronic myelogenous leukemia), likely contributed by concurrent morbidities).
  - If a patient experiences Grade 3 neutropenia (ANC $<1000$ ) or Grade 3 thrombocytopenia (platelets  $<50,000/\text{mm}^3$ ) with or without Grade 1 or 2 non-CNS hemorrhage, the treatment will be withheld. Counts should be checked twice weekly during this time. If the toxicity resolves to meet on study parameters within 14 days of drug discontinuation, the patient may resume treatment with the dose reduced as mentioned in Section 6.1. Treatment should resume 14 days from drug discontinuation even if toxicity has resolved before 14 days in order to allow for a full 2-week rest period before resuming drug.
  - If a patient experiences Grade 1 CNS hemorrhage or Grade 3 or  $>$  non-CNS hemorrhage, the treatment will be withheld. Treatment will not be resumed and the participant will discontinue study drug permanently.
  - If toxicity does not resolve to meet on study parameters within 14 days of drug discontinuation, the patient must be removed from protocol therapy.
  - If dose-limiting toxicity recurs in a patient who has resumed treatment at the reduced dose (maximum of 2 dose reductions allowed), the patient must be removed from protocol therapy.
  - Myeloid growth factors will not be used on study.
- 2. Dose modifications for non-hematological toxicity.**
  - If a patient experiences non-hematologic DLT as defined in Section 8, the treatment will be withheld. If the toxicity resolves to meet on study parameters within 14 days of drug discontinuation, the patient may resume treatment with the dose reduced as mentioned in Section 6.1 (see Appendix A). Treatment should resume 14 days from drug discontinuation even if toxicity has resolved before 14 days. Doses reduced for toxicity will not be re-escalated, even if there is minimal or no toxicity with the reduced dose.
  - If toxicity does not resolve to meet on study parameters within 14 days of drug discontinuation, the patient must be removed from study.
  - If dose-limiting toxicity recurs in a patient who has resumed treatment at the reduced dose level, the patient must be removed from protocol therapy.

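### Observation ends 30 days after the last dose rather than at Month 6, and clinical events are tested as counts with no time denominator, so early stoppers contribute shortened windows and patients who continue imatinib have no defined exit date

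*Combined protocol and SAP*

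**What the plan says.** Planned treatment is fixed in Section 6.0: "Patients will receive Imatinib orally once daily for 6 months". Study exit is not tied to that period. The first criterion in Section 14.0 is "Thirty days after the last dose of the investigational agent"; the others are death, loss to follow-up, withdrawal of consent and entry to another therapeutic study. Section 13.0 keeps a patient who is off therapy under follow-up only until one of these criteria is met. It adds "Follow-up data will be required unless consent is withdrawn" but gives no end date.

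Treatment can end early by several routes: toxicity (Sections 6.1 and 9.0), under 70% of prescribed drug taken (Section 13.0), or missed weekly contacts with no clinic visit in their place (Section 6.0).

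Section 4.3 takes hospitalizations, acute chest syndrome, parenteral opioid use and refills from the EMR, and vaso-occlusive crises (VOC) and oral opioid use from the patient diary. Section 5.1 compares clinical outcomes during treatment with those before it, the latter by chart review over an unstated period. Section 15.4 says: "Many secondary endpoints are counts (e.g. frequency of refills of opioids, number of hospitalizations", and offers McNemar's test on dichotomized data, a Cochran-Mantel-Haenszel type test, a paired t-test or a Wilcoxon signed rank test.

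On unresolved toxicity, Section 9.0 item 2 (non-hematologic) says: "If toxicity does not resolve to meet on study parameters within 14 days of drug discontinuation, the patient must be removed from study". The matching hematologic rule in item 1 removes the patient from protocol therapy only.

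On treatment after Month 6, Section 6.1 says: "Continuing treatment beyond this period will be at the discretion of the investigator".

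**The concern.** An event count depends on how long the patient is watched. The exit rule makes that time depend on when the drug was stopped, and the analysis section does not correct for it. The patients with the shortest windows are those who could not tolerate the drug, did not take it, or dropped out of contact. If their short counts are paired with a full baseline window, they look improved on aim 4.22 whatever the drug does. Section 2.0 says that the results will inform a later Phase II-B trial of clinical outcomes, so a spurious fall could be carried into that design.

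Two related gaps follow from the same exit wording. The documents disagree on whether unresolved non-hematologic toxicity ends treatment or participation. For a patient still taking imatinib after Month 6, the plan does not say when study participation ends or what the one-month post-treatment sample represents.

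**Working it through.** **The plan's own figure.** The plan gives no event rate, stopping rate or window length to reproduce. Its one power figure (89%, Section 15.1) concerns the primary test. The SD of the difference is 75,000 × √(2 × (1 − 0.5)) = 75,000, the noncentrality is (70,000/75,000) × √20 = 4.174, and df = 19. At two-sided alpha 0.01 this gives 88.98%, so the figure is reproduced. It does not bear on the event counts.

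**Inputs for the illustration**
- From the documents: six months planned, exit one month after the last dose, 20 patients with sickle cell anemia.
- Assumed: a constant rate of 2 events per year, the same for every patient, with no drug effect. This is the VOC entry minimum in Section 5.2.1; the documents give no rate for the EMR outcomes.
- Assumed: a six-month baseline window, events counted to study exit, and the number and timing of stops.

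**One patient stopping at month s.** Months observed to Month 6 = min(s + 1, 6). Expected events = 2 × months/12. Chance of any event (Poisson) = 1 − exp(−expected).

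| Stop month | Months observed | Expected events | Chance of any event | Apparent reduction |
|---|---|---|---|---|
| 1 | 2 | 0.33 | 28% | 67% |
| 2 | 3 | 0.50 | 39% | 50% |
| 3 | 4 | 0.67 | 49% | 33% |
| 4 | 5 | 0.83 | 57% | 17% |
| 5 or later | 6 | 1.00 | 63% | 0% |

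The fourth column is what a dichotomized McNemar comparison would see.

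**Group of 20 with k stoppers.** Fall in the mean count = (k/20) × (1 − (s + 1)/6). With one common rate, this does not depend on the rate.

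| k | Stop at month 1 | Stop at month 3 | Stop at month 5 or later |
|---|---|---|---|
| 2 | 6.7% | 3.3% | 0% |
| 4 | 13.3% | 6.7% | 0% |
| 6 | 20.0% | 10.0% | 0% |

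**False findings.** In a simulation with Poisson counts and no drug effect (paired t-test, two-sided 5%, 10,000 runs), the chance of a significant result in the drug's favour was 2.5% to 2.8% with no stoppers. With 4 stopping at month 1 it was 6.3%, 7.8% and 9.6% at 2, 4 and 6 events per year. With 4 stopping at month 3 it was 3.9%, 4.4% and 5.2%.

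**Toxicity wording, side by side.** Section 9.0 item 2 removes the patient from the study. Section 9.0 item 1 removes the patient from protocol therapy. Section 6.1 has patients who do not recover within 14 days stop study drug permanently. Section 13.0 keeps patients who are off therapy in follow-up. Section 14.0 does not list toxicity as a reason to leave. Item 2 is the odd one out.

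**Continuers.** Section 6.1 describes supply "for an exposure period of up to 6 months or so long as the patient remains on study" and then allows further treatment. It does not say whether drug taken after Month 6 is still the investigational agent for Section 14.0, so the 30-day clock has no defined start. The only post-drug sample is the visit that Section 6.0 calls one month off therapy and Table 2 calls one month off study. While a patient stays on imatinib, that sample is on-drug or absent.

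**The case against.** The strongest reply is that Section 15.4 does not say shortened counts will be set against a longer baseline. Aim 4.21 speaks of frequency, the baseline window is open, and matched windows or rates would remove the error. This stands. A reader might infer that the plan builds in a bias towards imatinib; the documents support only that it can arise, because nothing in the plan prevents it. Leaving the stoppers out is no remedy, since it replaces the short window with selection.

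A reader might also infer that patients with unresolved toxicity lose safety follow-up before 30 days. The documents do not support this. Section 13.0 requires ongoing adverse events to be followed, and Section 7 requires serious events to be reported to 30 days after the last dose. Section 13.0 item 1 itself uses removal from study as a reason to end therapy, so the wording in Section 9.0 may simply be loose. What remains is a mismatch to reconcile.

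Nor do the documents support saying that continuers never leave the study, or that they are the best responders. The other exit criteria still apply, the clock starts whenever the drug stops, and drug after Month 6 may not count as study drug. Nothing describes who will continue. The exit date is undefined, and no more than that.

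On importance, these are secondary outcomes in an uncontrolled 20-patient pilot, and stops at month 1 are close to the worst case. Both points stand and limit the weight of the concern. The same exit rule can also cost the Month 6 primary sample in early stoppers, but that is a separate question of power.

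**Conclusion.** The concern holds in conditional form. Exit is tied to the last dose, patients who stop before about month 5 have a shortened window, and the count analysis has neither a time denominator nor a stated baseline length. If shortened counts meet a longer baseline, the spurious fall in the group mean runs from zero (stops from month 5) through about 3% to 10% (month 3) to about 7% to 20% (month 1), for 2 to 6 stoppers of 20. These sizes rest on an assumed constant common rate, a six-month baseline, and assumed numbers and dates of stops. A longer unscaled baseline would make the comparison worse, for completers as well. A person-time analysis would remove the window error.

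The removal wording in Section 9.0 conflicts with Sections 6.1, 13.0 and 14.0 whatever the statistics. The gap for continuers affects only the descriptive post-treatment summaries; the primary test compares baseline with Month 6. The plan should be changed on these points, but they do not undermine the primary analysis.

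**What to change.** 1. Keep every treated patient on study for outcome collection until the later of 30 days after the last dose and the scheduled Month 6 date, unless consent is withdrawn.
2. Extract the EMR outcomes (hospitalizations, acute chest syndrome, parenteral opioids, refills) to Month 6 for all treated patients, and compare them with a pre-treatment window of the same length, stated in Section 15.4.
3. Analyse diary-based VOC and oral opioid use per person-time observed, because EMR extraction does not complete those counts after a patient stops keeping the diary.
4. Reconcile the removal wording in Section 9.0 item 2 with the hematologic rule and with Sections 6.1, 13.0 and 14.0.
5. For patients who continue imatinib after Month 6, state a study end date, flag the one-month sample as on-drug, report it apart from the off-drug summaries, and report how many continued. Give that visit one name and one timing in Section 6.0 and Table 2.

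The cost is protocol wording and a few more months of passive data on stoppers, from an EMR extraction that the sites already perform; no visits are added. The drawback is that counts to Month 6 include off-drug time and so answer a different question from events on treatment. On-treatment rates should therefore be reported alongside them. The off-drug sample set will be smaller, but every sample in it will be off drug.
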